### 3.3.4.2 Discontinuation of the trial by the sponsor

Boehringer Ingelheim reserves the right to discontinue the trial overall or at a particular trial site at any time for any of the following reasons:

1. New toxicological findings or serious adverse events invalidate the earlier positive benefit-risk-assessment. More specifically, the trial will be terminated if more than 50% of the subjects show drug-related and clinically relevant adverse events of moderate or severe intensity, or if at least one drug-related serious adverse event is reported that is considered to be unacceptable.
2. The expected enrolment goals overall or at a particular trial site are not met.
3. Violation of GCP, or the CTP, or the contract with BI by a trial site or investigator, disturbing the appropriate conduct of the trial.
4. The sponsor decides to discontinue the further development of the investigational product.
5. Inclusion of any new cohort, and the treatment of current cohorts will be stopped as soon as at least 2 subjects at one dose level on active drug showed relevant individual QT prolongation, i.e. a QTc increase of greater 60 ms from baseline in connection with absolute QT or QTc greater than 500 ms, which has been confirmed by a repeat ECG recording.
6. Inclusion of any new cohort, and the treatment of current cohorts will be stopped as soon as at least 2 subjects at one dose level on active drug shows AEs fulfilling stopping criteria ([Section 3.1](#)).
7. This multiple dose study is planned not to exceed the  $C_{max}$  or  $1/10^{th}$  of the AUC observed at NOAEL in the 4-week rat toxicity study as stated in [Section 1.2.3](#). For this reason preliminary PK assessments will be performed at each dose level before starting with the next cohort (not applicable at the 10 mg dose level).

The investigator / the trial site will be reimbursed for reasonable expenses incurred in case of trial termination (except in case of the third reason).

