The minimum data set for review consists of the following data:

- AEs in the current and, if applicable, preceding dose groups (including clinically relevant findings from ancillary safety testing listed below) (Note: AEs may be ongoing at the time of Safety Reviews and AE information may be subject to change prior to Database Lock)
- Results from 12-lead EGG in the current and preceding dose groups.
- Vital signs in the current and preceding dose groups
- Clinical laboratory tests in the current and preceding dose groups
- Check of criteria for stopping subject treatment as per [Section 3.3.4.1](#)
- PK data including extrapolation to support conclusions about safety margins (not required for inclusion of second cohort of the 10 mg dose group since based on the results from the previous SRD/MRD study (see [Section 1.2.5](#)) exposure is not expected to exceed  $C_{max}$  and 1/2 of the AUC of the 4-week rat toxicology study at NOAEL.

The decision to continue with the next cohort at the same dose level or the next higher dose level will be made jointly by the Principal Investigator (or an authorised deputy) and the trial clinical monitor (or an authorised deputy) based on the criteria described in [Section 2.3](#). In-depth analysis includes preliminary PK data, if possible extrapolations of exposure for the current and any new cohorts, all available safety data, especially SAEs (if occurred), AEs fulfilling stopping criteria, other AEs and out-of-range laboratory results (if considered clinically significant) and ECG results. Safety Reviews can be conducted face-to-face or by video/telephone conference. The trial clinical monitor is responsible for organizing and minuting the reviews. Minutes will be signed off by the Principal Investigator (or an authorised deputy) and filed in the ISF and TMF.

To proceed to the next higher dose level at least data up to Day 28 from 10 evaluable subjects of the preceding dose level (with at least 7 subjects on active treatment) are required.

The investigator (after consultation with the sponsor) is allowed to alter the scheduled dose levels within the planned dose range on the basis of experience gained during the study.

An overview of all relevant trial activities is provided in the [Flow Chart](#). For visit schedules and details of trial procedures at selected visits, refer to [Sections 6.1](#) and [6.2](#), respectively.

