### **3.2 DISCUSSION OF TRIAL DESIGN, INCLUDING THE CHOICE OF CONTROL GROUP**

For multiple-rising dose trials, the design described in [Section 3.1](#) is viewed favourable under the provision not to expose the subjects involved to undue risks since the main study objective is to investigate safety and tolerability of BI 1467335.

With the rising dose design, double -blind conditions regarding the subject's treatment (active or placebo) are maintained within each dose group. However, the current dose level will be known to subjects and investigators. The disadvantage of this trial design is a possible observer bias with regard to the dose-depending effects as well as time effects, but it has the virtue of minimizing subject risk by sequentially studying ascending doses. As time-effects are expected to be small relative to the differences between the doses in the broad range investigated, unbiased comparisons between treatments can still be expected.

It is standard in trials involving healthy volunteers to include a placebo group as control for the evaluation of safety, tolerability and pharmacodynamic effects. Each dose group consists of 12 subjects with 9 on active treatment, and 3 on placebo. The placebo control group includes all subjects of all dose groups treated with placebo. At the 10 mg dose level there will be a staggered inclusion of 2 cohorts of 6 subjects. At any higher dose level there will be a staggered inclusion of 3 cohorts each consisting of 4 subjects with 3 subjects randomized to active treatment and 1 subject randomized to placebo. The criteria to proceed with any new cohort are provided in [Section 2.3](#) and [Section 3.1](#).

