Description of change		
The amended protocol includes major changes. Since most of the changes apply to several sections throughout the protocol, the changes may be described only once and not repeated for each section:
 
 
1. Synopsis, Flowchart           
 
- Change of placebo (removal of quinine)
 
- Dose escalation steps modified to 10 mg, 15 mg and 20 mg, additional dose groups > 20 mg may be included taking into account predefined stopping criteria.
 
- Additional ECG recordings (including an ECG recording 15 minutes after dosing)
 
- 2 predose PD samples instead of only one sample
 
 
 
2. Section 1.2.5           
 
- Correction of maximum individual Tmax to 1.1 h (instead of 1.3 h)
 
 
 
3. Section 2           
 
- Deferred inclusion of subjects and implementation of more cohorts per dose group taking into account safety, tolerability and preliminary PK data
 
- Prespecified stopping criteria based on extrapolated PK data in the ongoing study (Cmax or 1/10th AUC at NOAEL of 4 week rat study should not be exceeded)
 
 
 
4. Section 3.1           
 
- Modified to comply with previous sections (Synopsis, Section 2)
 
 
 
5. Section 3.3.3.2           
 
- Additional exclusion criterion GFR based on CKD-EPI > 90 ml/min
 
 
 
6. Section 3.3.4.1           
 
- Additional stopping rules based on safety (such as eGFR calculated with the CKD-EPI formula < 80 ml/min; signs of rhabdomyolysis; threshold for
 
 
 

Number of global amendment		1

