To be implemented immediately in order to eliminate hazard – IRB / IEC / Competent Authority to be notified of change with request for approval		
Can be implemented without IRB / IEC / Competent Authority approval as changes involve logistical or administrative aspects only		
Section to be changed		
 
1. Synopsis
 
2. Section 2, Rationale, objectives and benefit-risk assessment
 
3. Section 3.1, Overall trial design
 
4. Section 3.3, Selection of trial population
 
5. Section 5.5.2, Methods of sample collection
 
6. Section 7.3.1 and 7.3.2 Attainment of steady state
 

Description of change		
Changes apply to several sections throughout the protocol and are described only once and not repeated for each section:
 
 
1. Deletion of dose groups > 20 mg QD.
 
2. Increase of the individual AUC threshold, which must not be exceeded by subjects, from 1/10th to 1/2 of the NOAEL in the 4 week rat study.
 
3. Additional Stability samples for the 15 mg Dose Group will be taken to assess more data
 

Number of global amendment
	
3
	
of the stability of the analyte in whole blood.          4. Attainment of steady state analysis via MMRM model changes to secondary analysis and nonlinear mixed model analysis added as primary analysis.

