
Rationale for change
		
The 10 mg dose group in this ongoing study 1386.8 has recently completed the 4 week treatment period. The evaluation is ongoing, preliminary data have become available. Overall, BI 1467355 was well tolerated. There were in particular no AEs considered to be dose limiting and no SAEs, all subjects completed the treatment period per protocol. There were no clinically relevant abnormalities with respect to safety laboratory, vital signs, or ECG. In particular there were no ECG findings suggesting adverse effects on the QT interval. Preliminary PK data obtained for the 10 mg dose level shows in all subjects an AUC exposure below Cmax and 1/10th of the AUC at NOAEL in the 1 month rats study, the initially defined exposure threshold not to be exceeded by subjects. Extrapolations based on the clinical PK data derived from the completed 10 mg dose group and the data obtained with the completed 2 week Phase I study suggest that with the next planned dose of 15 mg QD over 4 weeks some subjects may exceed the 1/10th AUC margin at the end of the 4 week treatment period. The estimated mean and the 95% prediction interval of Cmax extrapolation to 15 mg are still well below the Cmax at NOAEL. As steady state was not reached after 4 weeks of treatment with 10 mg BI 1467355 it is considered to be more appropriate to use a nonlinear fit for determination of the attainment of steady state. Additional data obtained with the 15 mg dose group are considered crucial to provide a safety margin regarding the assumed maximum efficacious dose of 10 mg QD in NASH patients. Since in the completed 10 mg dose group there were no safety signals precluding the continuation with the next higher dose it is considered to be justified to increase the initial exposure threshold from 1/10th AUC to ½ AUC at NOAEL obtained in the 4 week toxicology study in rats. It should

Number of global amendment		3
		be highlighted that all remaining stopping rules (individual discontinuation criteria or stopping rules for the whole study) will remain unchanged. In addition the study is conducted under close clinical monitoring (including central ECG reading) to early identify adverse safety signals. In context with the changes required for Amendment 3 a few remaining inconsistencies were also corrected.

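### Section 3.3.4.2 item 7 still plans to 1/10 of the rat NOAEL AUC, very likely a missed update after Amendment 3 raised the threshold to 1/2

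*Protocol*

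**What the plan says.** Section 3.3.4.2 lists the grounds on which the sponsor reserves the right to discontinue the trial. Item 7 says the study is planned to stay within Cmax or "1/10^{th}$ of the AUC observed at NOAEL in the 4-week rat toxicity study". It then links that limit to the cohort checks: "For this reason preliminary PK assessments will be performed at each dose level before starting with the next cohort", with the 10 mg level exempted.

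Section 3.1 names a different fraction of the same AUC. In its list of data for the Safety Review it explains why the second 10 mg cohort needs no PK data: exposure is not expected to exceed Cmax "and 1/2 of the AUC of the 4-week rat toxicology study at NOAEL".

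Section 11 gives the history. Amendment 1 brought in "Prespecified stopping criteria based on extrapolated PK data in the ongoing study", with the limit at Cmax or 1/10 of the AUC. Amendment 3, dated 05 OCT 2016 like this revision, records "Increase of the individual AUC threshold, which must not be exceeded by subjects", from 1/10 to 1/2. Its rationale says that at 15 mg "some subjects may exceed the 1/10th AUC margin at the end of the 4 week treatment period", and adds that "all remaining stopping rules (individual discontinuation criteria or stopping rules for the whole study) will remain unchanged".

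Section 3.2 sets the cohorts at each dose above 10 mg: "staggered inclusion of 3 cohorts each consisting of 4 subjects with 3 subjects randomized to active treatment". Section 7.3.4 plans at least seven preliminary PK analyses to keep exposure within margins that it takes from Section 2.3.

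**The concern.** Item 7 is among the sponsor's reasons to discontinue, and it is given as the reason for the PK checks before each next cohort above 10 mg. Those are the doses for which the margin was raised. If item 7 carries the old limit, the people deciding on a cohort at 15 or 20 mg hold two written values for one quantity. An exposure that the sponsor foresaw and accepted in Amendment 3 would still lie above the level at which item 7 says the study is planned to stay. The possible results are an argument over whether a cohort may start or continue, or a halt that the amended plan does not call for.

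**Working it through.** The limit is a chosen threshold and is not derived from other inputs, so there is no plan figure to reproduce. The check compares texts and then sizes the gap.

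**1. The statements side by side**

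| Place | Fraction of rat NOAEL AUC | Role |
|---|---|---|
| Section 3.3.4.2 item 7 (current) | 1/10 | Level the study is planned not to exceed |
| Section 3.1 (current) | 1/2 | Reference margin explaining the missing PK check at 10 mg |
| Section 11, Amendment 1 | 1/10 | Limit introduced |
| Section 11, Amendment 3 (date of this revision) | 1/10 raised to 1/2 | Threshold not to be exceeded by subjects |

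All four refer to the 4-week rat study and its NOAEL.

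**2. Which value is out of date**

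- The Amendment 3 rationale calls 1/10 the limit as initially defined, and says that raising it to 1/2 is justified.
- The stated reason is that some 15 mg subjects may pass 1/10. A plan to stay below 1/10 does not fit with going on to 15 mg on that expectation.
- Amendment 3 says its changes apply to several sections and are described only once. Its list of changed sections names 3.1, which now carries 1/2. It names 3.3 by its title but not 3.3.4.2, which Amendment 1 had named separately.

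The pattern fits an update that missed item 7.

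**3. Size of the gap**

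Ratio of the two values: 0.5 / 0.1 = 5. The disputed band runs from 0.10 to 0.50 of the NOAEL AUC. The Cmax limit is not in dispute.

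**4. Decisions affected (Section 7.3.4)**

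| Analysis | Cohort start supported |
|---|---|
| 1 (10 mg data, extrapolated to higher doses) | 15 mg, cohort 1 |
| 2 | 15 mg, cohort 2 |
| 3 | 15 mg, cohort 3 |
| 4 | 20 mg, cohort 1 |
| 5 | 20 mg, cohort 2 |
| 6 | 20 mg, cohort 3 |

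Cohorts above 10 mg: 2 dose levels × 3 = 6. Active-drug subjects: 6 × 3 = 18. Analyses 2, 3, 5 and 6 also support continuing cohorts already on treatment. Analysis 7 follows all 20 mg dosing and supports none of these starts. The 10 mg exemption does not remove analysis 1: Section 3.1 explains it as covering entry of the second 10 mg cohort, whereas analysis 1 supports the step to 15 mg.

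**5. Illustration of the band (assumed slope)**

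The protocol gives no dose-exposure slope. Assume AUC rises as dose to the power β, with β from 1 (dose-proportional) to 2. A subject at fraction f of the NOAEL AUC on 10 mg would pass a limit L at dose D if f > L / (D/10)^β.

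| | β = 1 | β = 2 |
|---|---|---|
| Pass 1/10 at 15 mg | 0.10/1.5 = 0.067 | 0.10/2.25 = 0.044 |
| Pass 1/10 at 20 mg | 0.10/2 = 0.05 | 0.10/4 = 0.025 |
| Pass 1/2 at 15 mg | 0.50/1.5 = 0.33 | 0.50/2.25 = 0.22 |
| Pass 1/2 at 20 mg | 0.50/2 = 0.25 | 0.50/4 = 0.125 |

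Amendment 3 reports that all 10 mg subjects were below 0.10. Over this assumed range, exposures like theirs could pass 1/10 at the higher doses while staying under 1/2. New subjects may differ, so this is not a bound. The conclusion rests on the sponsor's own statement about 15 mg.

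**The case against.** Several points on the other side carry weight.

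- **The two current sections can both be literally true.** Section 3.1 sets no limit at 1/2. It states an expectation for 10 mg, which is compatible with a plan to stay below 1/10. This stands. Without Amendment 3 the difference would only be suggestive. But the Amendment 3 entry carries this revision's date and explains the change that the revision was meant to make, so it is good evidence of the intended value.
- **The 1/10 may have been kept on purpose.** Amendment 3 calls the raised limit an individual one and leaves study-level stopping rules unchanged. This is the weaker reading. The unchanged rules are the remaining ones, which excludes the one just changed. Item 7 defines no separate group-mean limit, and a retained 1/10 would defeat the amendment's purpose. It cannot be ruled out entirely, hence very likely rather than certain.
- **Item 7 is not where cohort decisions are made.** Sections 3.1, 3.2 and 7.3.4 send the reader to Section 2.3 for the criteria or margins. That section is not shown, but Amendment 3 lists Section 2 as changed. This stands and lowers the practical risk.
- **The sponsor would hardly halt on a value it has just raised.** This is fair, but the decision to proceed is joint with the Principal Investigator, who reads the same text.

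A reader might infer that subjects could be over-exposed, or that the first 15 mg exposure above 1/10 forces a stop. Neither is supported: the stale value is the stricter one, and item 7 is a planning statement within a list of reserved rights. A reader might also infer that Section 2.3 is wrong, but nothing can be said about its wording.

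**Conclusion.** The point holds as an internal inconsistency in a decision threshold: item 7 is wrong as written and should be corrected. The choice of 1/2 itself is not challenged. The stated limit differs 5-fold from the amended one, leaving exposures from 0.10 to 0.50 of the NOAEL AUC in dispute. The affected analyses support the start of all 6 cohorts above 10 mg, with 18 planned active-drug subjects. That number counts subjects under an ambiguous clause; it does not measure harm. No endpoint or estimate changes.

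The conclusion assumes that Amendment 3 states the intended threshold for the whole protocol. If Section 2.3 gives 1/2, the decision makers have the right value there and the risk is smaller, but item 7 would still conflict with it.

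**What to change.** In Section 3.3.4.2 item 7, replace 1/10 with 1/2 and leave the Cmax limit and the rest of the item as they are. Confirm that Section 2.3 and the margins applied in the Section 7.3.4 preliminary PK analyses give the same value. If the sponsor did mean to keep 1/10 as a study-level limit, item 7 should say so and state how it relates to the individual threshold.

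The cost is one line of text, with no new data or subjects. It belongs in a protocol amendment, and Section 8.1 requires ethics committee and competent authority approval for changes introduced by amendments. The correction should be in place before the cohort decisions that it affects.

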## 4. TREATMENTS

### 4.1 TREATMENTS TO BE ADMINISTERED

The investigational product has been manufactured by BI Pharma GmbH & Co. KG.

#### 4.1.1 Identity of BI investigational product and comparator product

The characteristics of the test product are given below:

Substance: BI 1467335  
Pharmaceutical formulation: Powder for oral solution (PfOS)  
Source: BI Pharma GmbH & Co. KG, Germany  
Unit strength: 40 mg (target solution concentration BI 1467335: 0.5 mg/ml)  
Posology: 1-0-0  
Route of administration: p.o.  
Duration of use: 28 days q.d. dosing

BI 1467335 will be provided as a powder for oral solution in 100 mL amber glass bottles.

Solvent for reconstitution is Sucralose (4 mg/mL) and Menthol (2 mg/mL) solution provided in 100 mL clear glass vials.

Solvent for reconstitution will be used as placebo.

At the time of use, the oral solution for dosing will be prepared as detailed in the instruction given in [Appendix 10.1](#) using the PfOS and co-supplied Solvent for Oral Solution (SfOS).

The solvent for reconstitution will be transferred to an empty 100 mL amber glass bottle, which will be appropriately labeled:

Substance: Matching placebo  
Pharmaceutical formulation: Solvent for oral solution (SfOS)  
Source: BI Pharma GmbH & Co. KG, Germany  
Unit strength: Not applicable  
Posology: 1-0-0  
Route of administration: p.o.  
Duration of use: 28 days q.d. dosing

Solvent is Sucralose (4 mg/mL) and Menthol (2 mg/mL) solution provided in 100 mL clear glass vials.

#### 4.1.2 Method of assigning subjects to treatment groups

Prior to the screening visit, subjects will be contacted in writing and informed about the planned visit dates. The subjects willing to participate will be recruited to dose groups according to their temporal availability. As soon as enough subjects have been allocated to the first dose group, the following subjects will be allocated to the next dose level. Therefore, the allocation of subjects to dose cohorts is not influenced by trial personnel, but only by the subjects' temporal availability. As the study includes healthy subjects from a homogenous population, relevant imbalances between the dose groups are not expected.

The list of subject and medication numbers will be provided to the trial site in advance. The allocation of subjects to study subject numbers will be performed prior to the first administration of trial medication. For this purpose, the subjects will be allocated to a study subject number by the method 'first come-first served'. Once a subject number has been assigned, it cannot be reassigned to any other subject.

The randomisation procedure is described in [Section 7.5](#).

#### 4.1.3 Selection of doses in the trial

The doses selected for this trial cover the subtherapeutic as well as the estimated therapeutic range and include a safety margin (see [Section 1.2](#)).

#### 4.1.4 Drug assignment and administration of doses for each subject

The treatments to be evaluated are outlined in [Table 4.1.4: 1](#) below. The number of dose volume for placebo corresponds to the number of dose volume of the respective dose level.

Table 4.1.4: 1 BI 1467335 and placebo treatments, oral administration

Dose	Substance	Pharmaceutical form	Unit strength**	Dose volume per administration	Total daily dose**
1	BI 1467335	oral solution	0.5 mg/mL	20 mL (10 mg) q.d. for 28 days	10 mg
2	BI 1467335	oral solution	0.5 mg/mL	30 mL (15 mg) q.d. for 28 days	15 mg
3	BI 1467335	oral solution	0.5 mg/mL	40 mL (20 mg) q.d. for 28 days	20 mg
1-3	Placebo*	oral solution	--	identical to active treatment	--

\* Subjects receiving placebo are equally distributed across dose groups

\*\* Unit strength and dose refer to free base of BI 1467355

The oral solutions for dosing (active drug and placebo) will be prepared according to the instruction given in [Appendix 10.1](#) by pharmacists or qualified pharmacy staff members or qualified medical study personnel at the trial site under the responsibility of the investigator.

The trial medication will be administered to the subjects, while in a sitting position, as an oral dose together with about 240 mL of water under supervision of the investigating physician or an authorised designee. The so-called four-eye principle (two-person rule) should be applied for administration of trial medication and – if applicable – its preparation (e.g. reconstitution),

if correct dosage cannot be ensured otherwise. Administration will be performed following an overnight fast, which is to start no later than 10 h before the scheduled dosing.

To ensure a dosing interval of 24 h, the administration of trial medication should take place at the same time every day.

Subjects will be kept under close medical surveillance from the evening of Day -1 to the morning of Day 4, from the evening of Day 13 to the morning of Day 17, and from the evening of Day 27 to the morning of Day 29. During the first 2 h after drug administration, subjects are not allowed to lie down (i.e. no declination of the upper body of more than 45 degrees from upright posture except for medical examination), or to sleep. For restrictions with regard to diet see [Section 4.2.2.2](#).

